Official title: mNGS -Guided Antimicrobial Treatment Versus Conventional Antimicrobial Treatment in Early Severe Community-Acquired Pneumonia among Immunocompromised Patients (MATESHIP)

NCT number: 05290454

Document date:19/8/2022

Study protocol:

Participants in this study will be randomly allocated to receive mNGS-guided treatment based on both results of mNGS and conventional microbiological tests (CMT) (the experimental arm); or conventional treatment only based on the results of CMT (the control arm).

NO intervention arm: Conventional treatment group

In the conventional treatment group, clinicians will alter or confirm definitive treatment based on the results of CMT. Participants will undergo CMT using appropriate LRT specimens and other necessary specimens (such as blood, pleural fluid, urine, et al.). LRT specimens including endotracheal aspiration, bronchoalveolar lavage fluid (BALF), and protected specimen brush, will be obtained within 24 h of participants entering the ICU. Blood samples, mid-stream urine, pleural fluid, and other respiratory specimens will be collected as soon as possible after admission and, preferably, before antimicrobial therapy begins. CMT, including bacterial/fungal stains and cultures, single or multiple RT-PCR, blood culture, serum and urine pathogen-specific antigen tests, and serum pathogen-specific antibody tests, will be performed according to the consensus statement regarding the management of immunocompromised patients with CAP and participant conditions.

Experimental arm: mNGS- guided treatment group

In the mNGS-guided treatment group, clinicians will alter or confirm definitive treatment based on both mNGS and CMT results. Participants will undergo mNGS test using appropriate LRT specimens. CMT will also be carried out using appropriate LRT specimens and other necessary specimens (such as blood, pleural fluid, urine, et al.), as described for the control group. LRT specimens will be divided into aliquots and used for both mNGS tests and CMT.

Microbiological tests

Conventional routine microbiological tests will be performed in local laboratories. LRT samples for mNGS tests will be transferred to the same professional genomic laboratory independently by cold-chain transportation; the genomic laboratory will perform nucleic acid extraction, library construction, amplification and sequencing, bioinformatic analysis, and data interpretation. During our study period, the professional genomic laboratory will use the consistent mNGS detection protocol among the samples of enrolled patients. An independent multidisciplinary panel of senior experts, including one infectious disease specialist, an intensivist, and a microbiologist, independently adjudicate the causative microorganisms for each patient after reviewing the mNGS results and necessary clinical data.

Participants management

During hospitalization, participants will receive personalized therapy according to 2019ATS/IDSA CAP guidelines, Pneumonia Severity Index (PSI) score, and participants' conditions. Once participants combine with sepsis or septic shock, they will be managed according to International Guidelines for Management of Sepsis and Septic Shock 2021.

Statistical analysis plan:

(1) Statistical software: All statistical analysis is mainly conducted by SAS 9.4 and R 3.6.0.

(2)

1) Full analysis set (FAS): includes cases that have been randomly assigned to the group and have follow-up records. Cases missing main evaluation indicators or lost to follow-up will be excluded from FAS.

2) Per-Protocol set (PPS): it is a subset of the ITT data set, that is, all those who complete relevant observations according to the requirements of the plan and meet the following conditions, refer to those

whose compliance is between 80% and 120%, Did not seriously violate the research plan, completed all the visits, and completed the CRF, the main evaluation indicators and most other evaluation indicators are not missing.

3) Safety set (SS): All groups who have been randomized and used at least one diagnosis method constitute the safety set of this study. All safety information records from the subjects will be evaluated, including adverse events, serious adverse events, and abnormal changes in safety indicators that have clinical significance.

4) The efficacy indicators were analyzed by FAS and PPS population respectively. Safety analysis adopts SS population analysis.

5) Stratified analysis: According to the center, stratified analysis is carried out on the 28-day mortality rate, and mNGS-guided treatment are explored for related effects on the prognosis of patients with severe community-acquired pneumonia.

(3) Statistical analysis content

Statistical analysis content

1). General principles of statistical analysis

All statistical tests use two-sided tests. After P value is adjusted by FDT, Q value ≤ 0.05 will be considered as statistically significant (unless otherwise specified). The description of quantitative indicators will calculate the mean, standard deviation, median, minimum, maximum, lower quartile(Q1), upper quartile (Q3), and classification indicators to describe the number of cases and percentages of each category. The general comparison of the two groups will be analyzed by appropriate methods according to the types of indicators. The comparison of quantitative data between groups will be based on the data distribution using group t test (homogeneity of variance, normal distribution) or Wilcoxon rank sum test, The classification data uses the chi-square test or the exact probability method (if the chi-square test is not applicable), and the rank data uses the Wilcoxon rank sum test or the CMH test. Kaplan-Meier description, Log-rank test and Cox regression were used for the survival time data of the study subjects. The research results of each research center are evaluated by meta-analysis to evaluate the heterogeneity and the overall research merger effect. The potential confounding bias (treatment, service, management, etc.) of each research center is analyzed using a multi-layered mixed model.

2). Baseline and demographic characteristics

Summarize the number of enrollment and make a list of dropped cases. The size of the data set in each group, the distribution of cases in each center, the comparison of the total dropout rate, and a detailed list of the reasons for termination.

The demographic characteristics (age, sex, height, body mass index, vital signs, etc.), history of allergies, etc. of the subjects were statistically described. According to the numerical characteristics of the variables, the t-test/Wilcoxon rank sum test was used to compare the quantitative data of the two groups of subjects such as age, height, and body mass index; the chis-square test/exact probability method was used to determine the gender of the subjects, post medical history, allergy history and other categorical variables for comparison.

Analysis of dropped cases: Cases that meet the criteria for dropped cases and the subjects withdrew from the study should be included in the dropped case analysis. The total dropout rate between groups and the dropout due to adverse events were compared using the chi-square test.

3). Effectiveness analysis

(1) Baseline index: Describe the baseline of each curative effect index, refer to general statistical methods for the comparison method between groups. A stratified analysis was performed based on the

center.

(2) Main efficacy indicators: The relative change in SOFA score from randomization to day 5, day 7, day 10, or the day of ICU discharge/death; and the consumption of antimicrobial agents during ICU stay (expressed as defined daily doses). Simultaneous FAS analysis and PPS analysis.

(3) Secondary curative effect index

- ①days from randomization to initiation of definitive antimicrobial treatment
- ②overall antimicrobial agent use and cost;
- ③total cost of hospitalization;
- ④length of ICU stay;
- ⑤28- and 90-day mortality; and clinical cure rate.

For all the outcome indicators, first conduct independent evaluation in each research center in accordance with general principles. Then meta-analyze the research results of each research center. Assess the heterogeneity and the combined effect of the overall study. Finally, a multivariate stratified mixed model was used to adjust the potential bias.

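### No efficacy analysis keeps all randomised patients: the FAS removes incomplete or lost cases patient by patient, the PPS is narrower still, and the ITT set is named but never used

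*Combined protocol and SAP*

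**What the plan says.** The analysis sets are defined in section (2) of the Statistical analysis plan.

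- **FAS, item 1).** The set "includes cases that have been randomly assigned to the group and have follow-up records". It is then narrowed: "Cases missing main evaluation indicators or lost to follow-up will be excluded from FAS".
- **PPS, item 2).** It is described as part of an ITT data set, a term that appears nowhere else. Members must have acceptable compliance, no serious violation, and have "completed all the visits, and completed the CRF". In addition, "the main evaluation indicators and most other evaluation indicators are not missing".
- **Use of the sets, item 4).** "The efficacy indicators were analyzed by FAS and PPS population respectively". The safety set, which comes closest to everyone randomised, is reserved for safety.

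The Effectiveness analysis section repeats the FAS/PPS pairing for the two main indicators: relative change in SOFA, and antimicrobial consumption in the ICU as defined daily doses (DDD). Mortality at 28 and 90 days, clinical cure, costs, ICU stay and days to definitive treatment are secondary.

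For time-to-event data, General principles says "Kaplan-Meier description, Log-rank test and Cox regression were used for the survival time data of the study subjects", without naming a set. For dropouts the plan says "Summarize the number of enrollment and make a list of dropped cases" and "The total dropout rate between groups and the dropout due to adverse events were compared using the chi-square test". No missing-data method is given.

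**The concern.** Randomisation makes the arms comparable only for the whole randomised group. Here membership of both efficacy sets depends on what happens afterwards: whether values were recorded and whether contact was kept. Clinicians act on the mNGS result, so they know the arm. Withdrawal, loss or non-recording can therefore differ by arm and by prognosis.

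The rule also discards data that the trial holds. It removes a case from a set that serves every efficacy outcome, so a gap in one outcome costs the patient's observed values in the others. Comparing FAS with PPS cannot expose this, because the patients dropped from the FAS are missing from the PPS too. The centre-by-centre estimates, meta-analysis and mixed model name no other population, so they inherit the same selection. Comparing dropout rates may show unequal loss but does not correct it.

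**Working it through.** **Step 1. The sets side by side**

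| Set | Who is left out | Assigned to |
|---|---|---|
| ITT | not defined | nothing (parent of the PPS only) |
| FAS | no follow-up records; missing main indicators; lost to follow-up | efficacy |
| PPS | incomplete visits or CRF; missing main or too many other indicators; compliance outside 80-120%; serious violation | efficacy |
| Safety | randomised, but no diagnostic method used | safety |

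No row combines all randomised patients with efficacy.

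The plan states no sample size, event rate or dropout rate, so there is no figure to reproduce. **Every input below is assumed.**

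**Step 2. How many patients the rule could remove.** Let each of the two main indicators be missing with probability m, independently, and let a share l be lost to follow-up.

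- One missing indicator is enough: share excluded = 1 - (1-m)²(1-l).
- Both must be missing: share excluded = 1 - (1-m²)(1-l).

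| m | l | one is enough | both needed |
|---|---|---|---|
| 2% | 0 | 4.0% | 0.04% |
| 5% | 0 | 9.8% | 0.25% |
| 10% | 0 | 19.0% | 1.0% |
| 5% | 5% | 14.3% | 5.2% |

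With l = 0, handling mortality on its own would exclude nobody.

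**Step 3. False mortality difference when the arms are truly equal.** With true mortality p, share excluded e and mortality x among the excluded, FAS mortality in an arm is (p - e·x)/(1-e).

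- Equal exclusion q, with x differing between arms by D: the false difference is q/(1-q) × D, opposite in sign to D. For q = 5%, 10%, 15% this is 0.53, 1.11, 1.76 points at D = 10 and 1.05, 2.22, 3.53 points at D = 20.
- Unequal exclusion (5% v 10%, or 10% v 15%), with p from 20% to 40% and the same x from 10% to 60% in both arms: about -2.0 to +2.6 points. The sign can go either way.
- Equal exclusion and equal x: zero.

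**Step 4. Late loss, only if loss to follow-up is counted beyond day 28.** Patients lost later were alive at day 28, yet they leave the 28-day analysis while every death by day 28 stays. With 28-day mortality m₂₈ and a share l of day-28 survivors lost, FAS mortality = m₂₈/(m₂₈ + (1-m₂₈)(1-l)).

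- m₂₈ = 30%: l = 5% gives 0.30/0.965 = 31.1%; l = 15% gives 0.30/0.895 = 33.5%. The false difference is 2.4 points.
- The same losses give 1.9 points at m₂₈ = 20% and 2.7 at 40%.
- 10% lost in both arms gives 32.3% in each: no difference, but both are too high.

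**Step 5. What using observed vital status recovers**

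- In Step 4, 28-day status is known for everyone lost later, so the false 28-day difference disappears.
- In Step 3 at q = 10% and D = 20, suppose half of the excluded have known status. The remaining share is r = 5%. If D is the same in the known and unknown halves, 0.05/0.95 × 20 = 1.05 of the 2.22 points remain. If the whole difference lies in the unknown half (D = 40 there), 0.05/0.95 × 40 = 2.1 points remain.
- A simple known-status proportion does not work at day 90. Keep 30% dead by day 28 and loss of 5% v 15% of survivors, and assume 40% true 90-day mortality in both arms with loss unrelated to later death. Known-status mortality is (0.30 + 0.10 × 0.95)/(0.30 + 0.70 × 0.95) = 0.395/0.965 = 40.9%, against 0.385/0.895 = 43.0%. A false 2.1 points remain. Censoring at last contact avoids this under the same assumption about loss.

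**Step 6. SOFA and DDD.** The Step 3 expression in SD units gives 0.028 and 0.056 at q = 10%, and 0.044 and 0.088 at q = 15%, for D = 0.25 and 0.5 SD.

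**The case against.** The best defence is that few patients may be affected. Both main indicators are short-term: SOFA runs to day 10 at most, and DDD covers the ICU stay. The differential losses and prognostic gaps used above are illustrative, with no support in the document. That stands, and it limits any statement about size. It does not supply an all-randomised analysis.

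Three stronger readings are tempting, and the document does not support them.

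- **That one missing main indicator certainly removes a patient.** The wording is plural and there are two indicators, so the text leaves open whether one or both must be missing. Only if one is enough does a patient with SOFA recorded but DDD missing leave the SOFA analysis. If both are needed, far fewer patients are removed for missingness (0.25% instead of 9.8% in the 5% example).
- **That deaths are dropped from the FAS.** The SOFA definition accepts the day of ICU discharge or death as an endpoint, so neither event alone makes the indicator missing. The PPS requirement to complete all visits is silent on deaths.
- **That loss is counted to day 90.** No horizon is given. The Baseline section refers to criteria for dropped cases that this document does not contain, so a definition may exist elsewhere.

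One could also point to the ITT data set as evidence that an all-randomised population was intended. It may have been, but no analysis here uses it.

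**Conclusion.** The point holds on the text. Efficacy is confined to the FAS and PPS, both of which select patients after randomisation, and the exclusion is by patient rather than by outcome. A patient removed for missing main indicators, or for loss to follow-up, also leaves 28-day mortality when vital status is known. That holds whether one or both indicators must be missing.

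The size and direction of bias are unknown and may differ by outcome. On the assumed inputs the false mortality differences run from zero to about 3.5 points, in either direction, and those for SOFA or DDD are about 0.03 to 0.09 SD. These are illustrations, not estimates for this trial. The case for changing the plan rests on the wording: the rule governs every efficacy result, and where a value was observed its loss is wholly avoidable. Where a value is truly missing, the gain depends on the missing-data method.

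**What to change.** 1. Define one all-randomised (ITT) set, analysed by assigned arm, as the primary efficacy set. Reconcile the terms ITT, FAS and PPS.
2. Delete the FAS exclusions for absent follow-up records, missing main indicators and loss to follow-up.
3. Handle missingness separately for each outcome, including cure, costs, ICU stay and days to definitive treatment, using every observed value.
4. For 28-day mortality, use all known vital status. For 90-day mortality, use Kaplan-Meier estimates and Cox models with censoring at last contact, not a simple proportion among those with known status.
5. For SOFA and DDD missing while the patient is alive, prespecify one method compatible with the planned tests and centre-level analyses. Multiple imputation is one option; if chosen, pool an effect estimate with its standard error rather than Wilcoxon P values.
6. Add sensitivity analyses for informative missingness or loss, for mortality as well as for SOFA and DDD.
7. Report complete-case and PPS results as supportive only, and state that the PPS does not exclude patients because they died.

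The cost is SAP wording and extra analysis work. The missing-data method is harder to apply in centres with few patients. No new patients or data items are needed.

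### The per-protocol set requires every visit to be completed and does not say that patients who die stay in it, although by the plan's general rule mortality is analysed in that set

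*Combined protocol and SAP*

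**What the plan says.** The Statistical analysis plan, (2) item 2), defines the PPS as "all those who complete relevant observations according to the requirements of the plan and meet the following conditions". The conditions then listed admit those "whose compliance is between 80% and 120%, Did not seriously violate the research plan, completed all the visits, and completed the CRF", and the definition also requires that "the main evaluation indicators and most other evaluation indicators are not missing". Death is not mentioned in any of them.

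Item 4) of the same section says which sets are used: "The efficacy indicators were analyzed by FAS and PPS population respectively". It makes no exception for secondary indicators. Mortality at 28 and at 90 days is listed in (3), 3) Effectiveness analysis, under the secondary indices.

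The FAS in item 1) "includes cases that have been randomly assigned to the group and have follow-up records", and leaves out patients who lack the main indicators or are lost to follow-up. It does not require all visits.

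On compliance, the experimental arm is described as one in which "clinicians will alter or confirm definitive treatment based on both mNGS and CMT results", and under Participants management "participants will receive personalized therapy according to 2019ATS/IDSA CAP guidelines". No measure of compliance is defined.

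**The concern.** A patient who has died cannot attend a later visit. If the condition is applied as worded, membership of the PPS depends on surviving to the last visit, and the set is then used to compare mortality. Deaths in severe pneumonia among immunocompromised patients are foreseeable, and the SOFA indicator already provides for death in the ICU.

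Two things are at stake. PPS mortality would be understated in both arms. The PPS comparisons of the two main indicators, SOFA change and antimicrobial consumption in defined daily doses, would be made among patients selected on an outcome that occurs after randomisation. In addition, two analysts could build different sets from the same text, one keeping the deaths and one dropping them.

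**Working it through.** **Reading the text**

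1. The all-visits condition is separate from the non-missing condition; both must be met.
2. The SOFA indicator may end on the day of ICU death, so a patient who dies can have a main-indicator value. That helps with the non-missing condition but does not waive the all-visits condition.
3. The paragraph on dropped cases says "Cases that meet the criteria for dropped cases and the subjects withdrew from the study should be included in the dropped case analysis". It does not say whether a death is a dropped case, so it does not settle the matter.
4. Mortality enters the PPS through the general sentence in item 4). The Effectiveness analysis section repeats the instruction to use both sets only under the main indicators, but nothing there withdraws the general rule for the secondary ones.

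**Arithmetic (illustration only)**

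The plan has no figure to reproduce. Every input below is an assumption, because the documents give no visit schedule, mortality rate or timing of deaths.

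Let m be true 90-day mortality and f the share of those deaths that occur before the last visit (subscript 1 = mNGS, 0 = control). Apart from death, everyone is taken as eligible.

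- Share kept in the PPS = 1 − m·f
- PPS mortality = m(1 − f)/(1 − m·f)
- PPS odds = m(1 − f)/(1 − m), so OR in the PPS = true OR × (1 − f₁)/(1 − f₀)

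*Visits run to day 90 (f = 1).* PPS mortality is 0 in both arms whatever the true effect, and the risk ratio is undefined. At 40% control and 30% mNGS mortality, 60 and 70 patients per 100 remain.

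*Visits end earlier.* Take m₀ = 0.40 and m₁ = 0.30, so the true OR is (0.30/0.70)/(0.40/0.60) = 0.643 and the true risk difference is −10 points. With f₀ = 0.40, PPS control mortality is 0.24/0.84 = 28.6%.

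| Assumed timing of the benefit | f₁ | PPS mNGS mortality | Risk difference (points) | OR |
|---|---|---|---|---|
| Same early share in both arms | 0.40 | 0.18/0.88 = 20.5% | −8.1 | 0.643 |
| All before the last visit | 0.20 | 0.24/0.94 = 25.5% | −3.0 | 0.643 × 0.80/0.60 = 0.857 |
| All after the last visit | 0.533 | 0.14/0.84 = 16.7% | −11.9 | 0.643 × 0.467/0.60 = 0.50 |

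*No true effect.* With m = 0.30 in both arms, f₁ = 0.30 and f₀ = 0.50, PPS mortality is 0.21/0.91 = 23.1% (mNGS) against 0.15/0.85 = 17.6% (control), OR 0.70/0.50 = 1.40. With the shares swapped the OR is 0.71.

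The mortality level falls in every case. The comparison between arms may shrink, grow, stay the same on the odds-ratio scale, or show a difference where there is none. If death counts as completion, f plays no part and none of this happens.

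**The case against.** The strongest objection is that the authors probably did not mean to exclude deaths. The PPS is introduced through observations that the plan requires, and a visit after death cannot be required. The SOFA indicator accepts the day of death as an endpoint day and is to be analysed in both sets, which suggests that patients who die were expected in the PPS. A mortality of nearly zero would also be noticed. This reading is plausible, but no section states it, and the SOFA provision would work equally well if it served the FAS alone. So the gap remains, although it may never cause harm.

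It is also fair to say that selection after randomisation is common to per-protocol sets in general. Only the part due to death is specific to this wording.

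A reader might infer three stronger claims, none of which the documents support.

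- *The rule biases the treatment comparison in a known direction or by a known amount.* It depends on visit times and timing of deaths that the documents do not give, and the illustration moves either way.
- *The trial's mortality result is unsound.* The FAS analysis is planned as well, and the FAS has no all-visits condition.
- *The 80–120% window distorts a result.* The text shows only that compliance is undefined. An upper limit above 100% fits poorly with a comparison of diagnostic strategies and individualised therapy, but no effect on any result can be shown.

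**Conclusion.** The point holds as a minor defect in a stated rule. Followed to the letter, the PPS definition removes patients who die before the last visit from a set in which, by the plan's general rule, mortality is compared. PPS mortality is then understated in both arms, down to zero if the visits extend to the mortality horizon, and the PPS analyses of the main indicators are conditioned on survival.

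This rests on the literal reading of the visit condition and on item 4) covering the secondary indicators. The parallel FAS analysis limits the harm but does not make the PPS result sound. The undefined compliance window is a drafting gap and only a side note.

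**What to change.** Add to the PPS definition, before outcomes are seen by arm:

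1. A patient who dies is regarded as having completed all visits and CRF pages due up to death, and stays in the PPS if otherwise eligible.
2. Values that cannot be obtained because of death are not counted as missing indicators.
3. The PPS analysis is supportive of the FAS analysis.

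These are changes of SAP wording only. They need no new data, since deaths must already be recorded for the mortality indicators.

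As a side item, replace the 80–120% window with a stated yes/no criterion for adherence to the allocated diagnostic strategy, or drop it. Dropping it costs nothing. If it is replaced, choose a criterion that can be judged from data already recorded.

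### The mortality and cure comparisons commit to no baseline severity covariate, although SOFA at randomisation and age are collected, so they are less efficient than the data allow

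*Combined protocol and SAP*

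**What the plan says.** Mortality at 28 and 90 days and clinical cure are secondary outcomes (SAP, Effectiveness analysis, secondary index ⑤). Four parts of the SAP bear on how they are compared.

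- **Analysis sets, item 5), Stratified analysis:** "According to the center, stratified analysis is carried out on the 28-day mortality rate". Centre is the only factor named, and the stated purpose is exploratory.
- **General principles, binary outcomes:** "The classification data uses the chi-square test or the exact probability method (if the chi-square test is not applicable". No adjustment is mentioned.
- **General principles, survival time:** "Kaplan-Meier description, Log-rank test and Cox regression were used for the survival time data of the study subjects". No covariate is listed for the Cox model.
- **End of Effectiveness analysis, all outcomes:** each centre is evaluated separately and the centre results are meta-analysed. The last step reads: "Finally, a multivariate stratified mixed model was used to adjust the potential bias". No covariates are listed here either. The only examples given for a mixed model are in General principles: "The potential confounding bias (treatment, service, management, etc.) of each research center is analyzed using a multi-layered mixed model". They describe care at a centre, not the patient's condition at entry.

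Three baseline variables are mentioned elsewhere. SOFA at randomisation must exist, because a main indicator is measured from it: "The relative change in SOFA score from randomization to day 5, day 7, day 10". Age is among the baseline descriptors: "The demographic characteristics (age, sex, height, body mass index, vital signs, etc". The protocol's Participants management section mentions the "Pneumonia Severity Index (PSI) score", but only as a guide to therapy.

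**The concern.** In a randomised trial with a binary outcome, a baseline variable that predicts death accounts for part of the outcome variance. Leaving it out puts that part into the standard error of the risk difference. It also leaves any chance imbalance in severity between the arms in the estimate, and this matters more where the numbers are small, as in the planned centre-by-centre evaluations.

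Mortality is the outcome that item 5) singles out for exploring whether mNGS-guided treatment affects prognosis. At least two plausible predictors are already on file, so the loss could be avoided without collecting anything.

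An adjusted model whose covariates are left open also allows them to be chosen after the outcomes are known. The mortality result would then depend on a choice that the plan does not constrain.

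**Working it through.** **Step 1: does any mortality step commit to severity?** Item 5) uses centre. Chi-square and exact tests cannot take a covariate. Log-rank and Cox are named without covariates. The closing mixed model is named without covariates, and the only examples for a mixed model are centre-level care factors in an open-ended list. So no step commits to severity, and none excludes it.

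**Step 2: inputs for the size.** The documents give no sample size, number of centres, mortality rate, effect size or prognostic strength, so there is no figure of the plan's own to reproduce. Everything below is assumed: one standardised normal severity score, a logistic model for death, overall mortality of 25% to 45% and an AUC of 0.60 to 0.78.

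**Step 3: formulas.** With individual risk p(x) and mean risk p:

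- explained share R² = Var[p(x)] / [p(1 − p)]
- SE ratio, adjusted to unadjusted risk difference = √(1 − R²)
- equivalent gain in patients = 1/(1 − R²) − 1

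**Step 4: results.**

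| Mortality | AUC | R² | SE ratio | Gain in patients |
|---|---|---|---|---|
| 25% | 0.60 | 0.024 | 0.988 | 2% |
| 40% | 0.65 | 0.067 | 0.966 | 7% |
| 40% | 0.70 | 0.118 | 0.939 | 13% |
| 40% | 0.75 | 0.184 | 0.903 | 23% |
| 45% | 0.78 | 0.234 | 0.875 | 30% to 31% |

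For the third row: √(1 − 0.118) = 0.939 and 1/0.882 − 1 = 0.134.

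**Step 5: translation to power.** Take 40% versus 30% mortality with 356 per arm, which gives 80% power unadjusted at two-sided 0.05 (before the SAP's multiplicity adjustment). Replacing n by n/(1 − R²) gives 82% at R² = 0.05, 84% at 0.10, 86% at 0.15 and 88% at 0.20.

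**Step 6: is there still a gain when centre is already in the model?** A simulation used 712 patients, 10 assumed centres with modest differences between them, and 2000 runs per row. It compared centre alone with centre plus severity. The risk difference came from linear regression with robust standard errors.

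| Log-odds slope of score (AUC) | SD of risk difference, centre only | SD, plus severity | Power, centre only | Power, plus severity |
|---|---|---|---|---|
| 0.55 (about 0.65) | 3.56 points | 3.47 points | 84% | 86% |
| 0.83 (about 0.70 to 0.72) | 3.49 points | 3.25 points | 80% | 85% |
| 1.2 (about 0.77) | 3.60 points | 3.24 points | 72% | 81% |

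The SD falls by about 3%, 7% and 10%.

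**Step 7: the odds-ratio scale.** In the middle row the mean log odds ratio moves from −0.451 (SE 0.162) to −0.513 (SE 0.173). The SE rises, but the conditional effect lies further from zero: 0.451/0.162 = 2.78 against 0.513/0.173 = 2.97. Power goes from 80% to 85%, while the interval does not narrow.

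**The case against.** The strongest reply is that an adjusted analysis is already planned. The closing mixed model applies to every outcome and is multivariate, and Cox regression is named as well. A reader of item 5) might infer that mortality is adjusted for centre and nothing else, or that severity has been excluded. The documents do not support that: severity is unspecified, and the list of mixed-model examples is open-ended. What remains is that a model with no covariate list does not commit the analysis to anything. The methods that are stated fully are the unadjusted and centre-stratified ones.

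Other parts of the reply also stand.

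- **PSI.** One might infer that PSI is available as a covariate. The protocol says only that it guides therapy, not that it is recorded as trial data or scored at baseline.
- **Bias.** One might infer that the mortality result is biased. It is not: randomisation leaves the unadjusted risk difference unbiased, and the loss is of efficiency.
- **Predictive strength.** Everyone enrolled has severe pneumonia and is in the ICU. That narrows the range of severity and could weaken the score. With an AUC of 0.60 to 0.63 the gain is only about 2% to 6%. The documents do not establish that severity predicts death better than centre does.
- **Sparse centres.** Fixed centre terms in a logistic model can fail where a small centre has no deaths or only deaths.
- **Role of the outcome.** Mortality is secondary, item 5) is exploratory, and the main indicators are untouched.

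**Conclusion.** The point holds as one about efficiency and pre-specification for secondary outcomes. No stated mortality or cure analysis commits to a patient-level covariate, while SOFA at randomisation and age are collected. Under the assumed AUC of 0.60 to 0.78 and mortality of 25% to 45%, adjustment is worth about 2% to 30% more patients on the risk-difference scale, which is a standard error about 1% to 12% smaller. The low end is negligible and the high end is material. The documents cannot say where this trial lies, because they give neither event rates nor the prognostic strength of SOFA or age.

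The narrower interval applies to the risk difference. On the log-odds scale the benefit is power alone. The change is worth making because it costs little even if the gain proves small, and because it closes an open choice of covariates.

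**What to change.** For 28-day mortality, 90-day mortality and clinical cure, make the pooled comparison one logistic regression per outcome with treatment, centre, SOFA at randomisation and age, all fixed before database lock. Enter centre as a random effect, or pool small centres by a stated rule, to avoid separation. Report the standardised (marginal) risk difference with its 95% CI, so that the estimate refers to the whole trial population. For survival time, use a centre-stratified Cox model with the same two covariates. Use PSI only if it is recorded at baseline.

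State that this model is the adjusted model called for at the end of Effectiveness analysis, and that it is the definitive mortality analysis. That avoids adding a further competing result to the existing sequence. Keep the by-centre rates in item 5) and the unadjusted rates as descriptive tables.

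The cost is a few lines of SAP text and one model per outcome, with no new data. The downsides are a simple imputation rule for rare missing baseline values and some care with sparse centres.
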